1. OBJECTIVES

In this study, we hypothesize that CBCT-guided NB would improve diagnostic yield for peripheral lung nodules as compared to NB alone. We aim to find the difference in the diagnostic yield between both groups (Percentage of lesions tested positive).

μ_0 = Diagnostic yield NB-alone = Diagnostic yield CBCT-guided NB μ_1 = Diagnostic yield CBCT-guided NB > Diagnostic yield NB-alone
 μ_0 = Null Hypothesis
 μ_1 = Alternate Hypothesis

1.1 Study Design

- We propose a prospective, randomized, two- arm, single-center nonblinded, controlled clinical trial to evaluate the diagnostic yield of lung biopsy in NB-alone and CBCT-guided NB.
- Randomization schedule will be determined in advance by computer with the intent of a 1:1 randomization scheme.
- For randomization, Block randomization will be used. The block randomization method is designed to randomize subjects into groups that result in equal sample sizes. This method is used to ensure a balance in sample size across groups over time. This was decided based on the limited access to the Cone Beam room, which is available exclusively once a month (the first Friday of each month).
- All bronchoscopies will be performed under general anesthesia and ROSE will be available upon physician request/preference.
- Radial probe-EBUS and fluoroscopy will be utilized in all cases.
- Tissue samples will be obtained using multimodality tools, including cytology brush, fine needle for aspiration, biopsy forceps, and bronchoalveolar lavage.
- NB procedure will be performed per product instructions and the institution's standard practice.

CBCT-guided NB procedure arm:

Following intubation, an inspiratory breath-hold maneuver with the adjustable pressure limiting (APL) valve set at 20 cm H₂O will be performed by the anesthesiology provider. This mimic the inspiratory

breath hold done during a CT scan. During the breath-hold maneuver, CBCT will be performed. A dedicated arm attached to the bronchoscopy cart will be utilized to hold the bronchoscope in position so that the operators can leave the room during CBCT scan. Lung nodules will be highlighted using available software (OncoSuite; Philips) during a process known as segmentation. A bronchoscope will be introduced into the airway and then using NB to navigate to the lesion. Nodule segmentation will be visualized in an overlay with live fluoroscopy. Geometric correspondence of augmented fluoroscopy (AF) will be maintained throughout the case while manipulating C-arm angulation, table position, and image-zoom settings. Final catheter position will then be verified in multiple planes with AF. Additional CBCT scans will be acquired when deemed necessary.

If a non-diagnostic lesion resolved, stayed stable or decreased in size on follow-up CT for at least 6 months after the index procedure then this will be as presumed benign and classified as a true negative for the purposes of calculating sensitivity and prevalence of malignancy, as well as for diagnostic accuracy.

1.2 Primary Objectives

- To compare overall diagnostic yield following biopsy of peripheral pulmonary nodules in the NB alone group versus the CBCT-guided NB group.

1.3 Secondary Objectives

- To compare the need of additional diagnostic procedures in both groups.
- To compare navigation success in the CBCT-guided NB group.
- To compare complications between groups

2. BACKGROUND

2.1 Study Disease

Diagnostic sampling of suspicious peripheral lung nodules has become increasingly important, as early diagnosis of malignancy can provide an opportunity for potentially curative resection and improved survival. Traditionally, CT-guided transthoracic needle aspiration (TTNA) was the most accepted modality to obtain tissue diagnosis of suspicious peripheral lung nodules, with a diagnostic yield reported in the literature ranging from 77 to 98% (1–4). However, despite the high diagnostic yield, pneumothorax can occur in up to 35% of patients, with up to 15% requiring chest tube placement, increasing hospital stays and overall healthcare costs (5,6). In contrast, the transbronchial approach the risk of pneumothorax is only around 0.02% to 4.9% (7–10). Furthermore, CT-guided TTNA might be associated with a higher incidence of local recurrence with pleural dissemination when compared with transbronchial or open lung biopsy (11).

Transbronchial biopsy is a safe diagnostic tool recommended for patients with peripheral lung nodules with the limitation of a lower diagnostic yield compared with CT-guided TTNA. The diagnostic yield of transbronchial biopsy guided by fluoroscopy is widely variable, ranging from 18 to 80%, and is strongly dependent on the lesion size (12,13). In order to increase the diagnostic yield of the transbronchial

approach, techniques and devices such as the ultrathin bronchoscope, radial endobronchial ultrasonography with guided sheath (EBUS-GS), electromagnetic navigation bronchoscopy and cone beam CT (CBCT) are becoming widely utilized (11).

ENB allows bronchoscopists to safely navigate to and sample peripheral lung lesions minimally invasively with an acceptable safety profile. Furthermore, the ability to provide concurrent lymph node staging with linear endobronchial ultrasound (EBUS) or assist in nodule localization via pleural dye or fiducial marking in a single procedure could potentially decrease health care costs and improve patient satisfaction (10). However, due to CT to body divergence and atelectasis, increasing diagnostic yield has been an ongoing challenge. Recently, cone beam CT (CBCT) has emerged as a promising adjunct to navigational bronchoscopy, allowing real-time “needle in lesion” static confirmation, with a potential increase in diagnostic yield (14).

2.2 IND Agent(s)

N/A

2.3 Other Agent(s)

N/A

2.4 Rationale

Pulmonary nodules are a common diagnostic problem in daily clinical practice. The results of the National Lung Cancer Screening Trial demonstrated a reduction in lung cancer mortality with screening of patients with low dose CT (15). This has led to an increase in the number of nodules detected requiring appropriate follow up (16). The challenge in the management of pulmonary nodules lies in the necessity to identify the few lung cancers within the vast majority of benign nodules. This created a dilemma for clinicians to decide about further diagnostic modalities to pursue for optimizing yield, minimizing complications while reducing unnecessary benign surgical resections rates. Thus, there is an urgent need for minimally invasive diagnostic techniques with both excellent performance and safety for evaluation of lung nodules. The overall diagnostic yield of currently available electromagnetic navigation bronchoscopy (ENB) technique is 67% based on meta-analysis of 11 studies (17). However, when analyzed more closely, the diagnostic yield appears to be influenced by nodule size and presence of a bronchus sign and it appears to be much lower approaching 47% (7). However, a major limitation of all ENB platforms is the reliance on preoperative CT for planning and navigation as opposed to real-time image guidance. This commonly results in CT body divergence leading to disappointing yields on navigational bronchoscopy. Cone beam computed tomography (CBCT) is a newer modality that emerged as a promising adjunct to navigational bronchoscopy that might mitigate CT to body divergence allowing near real-time confirmatory imaging, with a potential impact on diagnostic yield. However, data on the use of this technology in combination with bronchoscopy is very scant and mostly based on non-randomized studies (18–20).

2.5 Correlative Studies Background

N/A

3. SUBJECT SELECTION

Adult patients who will be referred to our clinic (Interventional Pulmonology) for diagnosis of lung nodules of 1–3 cm identified on chest CT scan obtained within the previous 3 months.

3.1 Subject Screening and Recruitment

The subjects for this study will be recruited consecutively from the investigators' clinical practices. The screening requirements are all standard of care for bronchoscopy procedures. No pre-procedure test or examinations outside of standard of care are required for this study.

All subjects who are eligible based on the inclusion and exclusion criteria will be asked to participate in this study. Subjects will then sign an IRB-approved consent form.

A subject will be considered enrolled when the following occurs:

1. Subject provides consent for participation by signing the current, IRB approved study informed consent form
2. Subject meets all eligibility criteria

3.2 Informed Consent

The principal investigator (PI) or Co-Investigator will conduct the informed-consent process. The PI/Co-Investigator will explain the nature and scope of the trial and potential risks and benefits of participation and will answer any questions from the subjects. If the subject agrees to participate, the informed-consent form must be signed and dated by the subject and the PI/Co-Investigator prior to enrollment in the study..

3.3 Eligibility Criteria

- 1) Patients ≥ 18 years old.
- 2) Patients with lesions having an intermediate pre-test probability of malignancy (pCA, 0.05 to 0.65) as determined by Swensen-Mayo nodule risk calculator and in whom bronchoscopic biopsy was determined to be the next best treatment step by the treating pulmonologists
- 3) Patients with higher risk lesions (pCA > 0.65) in need of a diagnosis for nonsurgical treatment or prior to surgery.
- 4) Patients are willing and able to provide informed consent.

3.4 Exclusion Criteria

- 1) There is a predetermined plan to pursue stereotactic body radiation therapy (SBRT) in the event of a nondiagnostic study procedure in patients with a nodule in the outer 1/3 lung zone (i.e. The patient would not go on for a CT guided TTNA).
- 3) Lacked fitness according to physician judgement to undergo bronchoscopy.
- 4) Contraindication for temporary interruption of the use of anticoagulant therapy. 5) Uncontrolled or irreversible coagulopathy.

- 6) Known allergy for lidocaine.
- 7) Uncontrolled pulmonary hypertension.
- 8) Recent (< 4 weeks) and/or uncontrolled cardiac disease.
- 9) Compromised upper airway (eg concomitant head and neck cancer or central airway stenosis such that endobronchial access is considered unsafe).
- 10) ASA classification ≥ 4
- 11) COVID-19 positive patient at the time of procedure.

3.5 Inclusion of Women and Minorities

Both men and women of all races and ethnic groups are eligible for this trial. Except for pregnant women as CT scan is generally contraindicated during pregnancy.

3.6 Subject Study Assessments

Pre-procedure Assessment

A pre-procedure assessment will be performed for each subject enrolled in the study in accordance with standard of care for bronchoscopy procedures. Trained study staff will review the data from available or indicated diagnostic tests confirming the subject's eligibility for study, (i.e. pre- procedure CT scan and laboratory tests), inclusion-exclusion criteria review, and perform an assessment of their medical history. For subjects of child bearing potential, a biochemical (blood or urine) pregnancy test must be obtained prior to the study procedure, per standard practice. If a subject's pre-procedure CT scan was obtained more than 21 days prior to the expected procedure date, a more recent CT scan should be obtained.

Intra-procedure Assessment

Procedure details, including the ability of the investigator to reach a pre-planned target location and obtain a tissue sample will be collected. Procedure durations, such as the total procedure time, anesthesia time, fluoroscopy time and navigation time are among those that will be collected. In addition, the ability to facilitate sampling through the catheter instrument, need for conversion to an alternative biopsy approach or surgery, Rapid On-site Evaluation (ROSE) results and intra- procedural complications (i.e. pneumothorax, bleeding, estimated blood loss and airway damage) will be obtained.

Post-procedure (prior to discharge) Assessment

The following outcomes will be collected: length of stay (bronchoscopy suite or hospitalization) and procedure related complications. Of note, per standard practice, subjects will be required to undergo a chest x- ray at least 1-hour post-procedure but prior to discharge to assess for pneumothorax.

Post-procedure (10 ± 4 days) Assessment

For patients that continue in the study due to a benign or non-diagnostic biopsy. This visit may be completed as a hospital visit, virtual visit or telephone contact. Any potential procedure-related complications will be recorded; in addition, the diagnostic characteristics of the obtained sample, initial pathology result and disease assessment will be obtained. If a subject has undergone any additional diagnostic interventions or treatment related to their pulmonary nodule, data regarding their interventions will be collected for the study but information related to complications will not be collected.

Post-procedure (30 ± 7 days) Assessment

For patients that continue in the study due to a benign or non-diagnostic biopsy, information related to any additional procedural complications (i.e. pneumothorax or pneumonia) will be collected.

Post-procedure (up to 180 days) Assessment

For patients that continue in the study due to a benign or non-diagnostic biopsy. Pathology and disease information will be obtained from any additional diagnostic assessments, interventions or treatments associated with the study related nodule(s).

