7 ADVERSE EVENTS: LIST AND REPORTING REQUIREMENTS

An adverse event (AE) is any untoward medical occurrence, unintended disease or injury, or untoward clinical signs (including abnormal laboratory findings) in subjects, users or other persons, whether or not related to the investigational medical device. All device and/or procedure related adverse events will be recorded. Events will be collected at the initiation of the index procedure (EBUS), intra-EMN procedures, and for a period of 30 days post-procedure.

Serious Adverse Events (SAE) are those that lead to death or lead to serious deterioration in the health of the subject (i.e. life-threatening injury/illness, permanent impairment of a body structure, leading to prolonged hospitalization). The PI will assess if there is a relationship of an adverse event to the procedure, as related or not related, and categorized as resolved or continuing. Severity of the common complications of pneumothorax and hemorrhage (including hemoptysis) will be classified according to Common

Terminology Criteria for Adverse Events (CTCAE).

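### Complications of follow-on diagnostic procedures are excluded at day 10, ambiguous at day 30 and uncollected afterwards, and the omission is linked to arm

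*Combined protocol and SAP*

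**What the plan says.** Section 1.3 lists the secondary objective "To compare complications between groups" and, separately, a comparison of the need for additional diagnostic procedures. Neither Section 1.3 nor Section 13.6 confines complications to the index bronchoscopy.

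Section 3.6 sets three contacts after discharge. Their scope is the same: "For patients that continue in the study due to a benign or non-diagnostic biopsy".

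- **10 ± 4 days.** Potential procedure-related complications are recorded. For patients who have had a further intervention or treatment for the nodule, however, "data regarding their interventions will be collected for the study but information related to complications will not be collected".
- **30 ± 7 days.** Here "information related to any additional procedural complications (i.e. pneumothorax or pneumonia) will be collected". The procedure concerned is not named.
- **Up to 180 days.** Later assessments, interventions and treatments contribute pathology and disease information. Complications are not mentioned.

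Section 7 states: "All device and/or procedure related adverse events will be recorded". Its window is: "Events will be collected at the initiation of the index procedure (EBUS), intra-EMN procedures, and for a period of 30 days post-procedure". It does not restrict collection by biopsy result.

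Section 13.1 names surgery, CT-guided TTNA and repeat imaging as ways to confirm a diagnosis after a non-diagnostic result. Section 2.1 says of CT-guided TTNA that "pneumothorax can occur in up to 35% of patients, with up to 15% requiring chest tube placement", against 0.02% to 4.9% pneumothorax for the transbronchial approach.

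**The concern.** Follow-on procedures arise mainly because the index biopsy did not give an answer, and the trial is built on the expectation that this happens more often with NB alone. A rule that records the second procedure but not its harm therefore removes more events from one arm than from the other. A reader of the final complications table could take it as the safety of each diagnostic strategy, when it covers only part of the pathway.

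The conflicting wording adds a second difficulty. Whether a pneumothorax after an early TTNA enters the data depends on which passage the study team follows, and the trial is not blinded.

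Third, contacts that depend on the biopsy result make the search for late complications of the index procedure depend on it too. That works in the opposite direction: patients in the lower-yield arm are contacted more often, so more of their late index complications may be found. The two effects cannot be assumed to cancel.

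**Working it through.** **Step 1: what is collected, by time**

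| Period | Follow-on procedure recorded? | Its complications recorded? |
|---|---|---|
| 10-day contact (3.6) | Yes | No, by explicit rule |
| 30-day contact (3.6) and Section 7 | Not addressed | Unclear: procedural complications are collected, procedure not named |
| After that, to 180 days (3.6) | Yes | No provision |

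**Step 2: the plan's own sample size**

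Inputs: control yield 67% (Section 13, from a meta-analysis of 11 studies); target difference 20 points, so 87% with CBCT; two-sided alpha 0.05, power 80%, uncorrected chi-squared test (13.2).

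n per arm = [1.96 × √(2 × 0.77 × 0.23) + 0.842 × √(0.67 × 0.33 + 0.87 × 0.13)]² / 0.20² ≈ 68.3, or 69 rounded up. The plan has 68, with power 79.8%. The yields of 67% and 87% therefore fit the design and can be used below.

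**Step 3: expected non-diagnostic results**

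- NB alone: 68 × (1 − 0.67) = 22.4
- CBCT-guided NB: 68 × (1 − 0.87) = 8.8
- Difference 13.6; ratio about 2.5

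**Step 4: follow-on pneumothoraces**

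Expected events = non-diagnostic patients × share going to TTNA × pneumothorax rate. The documents do not give the share, so all three values are assumptions. The 35% rate is the cited upper figure; the 15% rate is an assumption.

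| Share to TTNA | At 35% (NB alone vs CBCT) | At 15% (NB alone vs CBCT) |
|---|---|---|
| 25% | 2.0 vs 0.8 | 0.8 vs 0.3 |
| 50% | 3.9 vs 1.5 | 1.7 vs 0.7 |
| 100% | 7.9 vs 3.1 | 3.4 vs 1.3 |

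For example, 22.44 × 0.50 × 0.35 = 3.9. Chest tubes at the cited upper 15% give the same figures as the right-hand column. All these events go uncounted if the 10-day rule governs throughout. If the 30-day wording is read broadly, only the later ones do. The documents do not say when follow-on procedures occur.

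**Step 5: index pneumothoraces**

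At the cited upper transbronchial rate: 68 × 0.049 = 3.3 per arm, or 6.66 in both arms. With both sources at their upper rates, follow-on events exceed index events across the trial only if the TTNA share is above 6.66 / [(22.44 + 8.84) × 0.35] = 6.66 / 10.95 = 61%.

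**Step 6: what a comparison could show**

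At the upper rates and a 100% share, the totals are 3.3 + 7.9 = 11.2 vs 3.3 + 3.1 = 6.4 events (16.4% vs 9.5%). Power with 68 per arm is about 23%.

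**The case against.** The strongest defence is that the plan compares harms of the study bronchoscopy and treats downstream burden as a separate objective, for which follow-on procedures are counted. Section 7 is built around the index procedure. That is a legitimate scope if it is declared. It is not declared: Sections 1.3 and 13.6 leave the scope open, and only one sentence under one contact narrows it.

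A second defence is that the 30-day contact and Section 7 already capture follow-on events. They can be read that way, and this part stands: a reader might infer from the 10-day rule that the plan rejects all such data, and the documents do not support that. But this reading contradicts the 10-day rule and leaves events after 30 days uncovered.

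A reader might also infer that sparing patients TTNA harm is the trial's stated rationale. It is not. Section 2.1 compares TTNA and the transbronchial route as alternative approaches, and Section 2.4 rests on CT-to-body divergence and yield. TTNA as a follow-on route comes from Sections 3.4 and 13.1, and the link to harm is an inference from the cited rates.

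Nor should misattribution of early pneumothoraces be pressed. A chest x-ray is required before discharge, the 10-day contact records procedure-related complications, and the investigator judges relatedness. What remains is a delayed index event in a patient who has already had a second procedure.

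Finally, the numbers are small and the larger ones combine upper limits. That is correct, and it limits what can be claimed about size. It does not justify an incomplete count.

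**Conclusion.** The point holds, as an arm-related gap and an internal conflict in the collection of complications. Under the planned yields, about 22 vs 9 patients are at risk of a follow-on procedure because of a non-diagnostic result. The follow-on pneumothoraces concerned range from 0.8 vs 0.3 to 7.9 vs 3.1, a between-arm difference of about 0.5 to 4.8 events, against at most about 3.3 index events per arm. The direction rests on the trial's own hypothesis; the size rests on an assumed TTNA share and, for the upper figures, on a rate cited as a maximum.

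A reader might conclude that most pneumothoraces in the trial would come from follow-on biopsies. The documents do not establish this: with both sources at their upper rates it needs a TTNA share above about 61%, and no share is given. Nor would complete counts support a formal safety conclusion; the comparison stays descriptive. The primary endpoint and its sample size are unaffected.

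**What to change.** 1. Reconcile the 10-day, 30-day and 180-day text of Section 3.6 with Section 7, and delete the sentence excluding complications.
2. For each follow-on diagnostic procedure already being recorded, also record complication type, date and the procedure that it followed.
3. State in Section 13.6 that two results will be reported by assigned arm, descriptively: (a) index-procedure complications to 30 days; (b) complications of all diagnostic procedures on the study nodule to 180 days, tabulated by procedure type so that surgery stays distinct from TTNA, and excluding complications of treatment.
4. Put the 30-day complication query to all randomized patients, as Section 7 implies, so that ascertainment does not depend on the biopsy result.

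The cost is a few case report form fields, some chart review for procedures done elsewhere, and a 30-day query for patients with a malignant diagnosis, whom the Section 3.6 contacts do not cover.

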10 STUDY CALENDAR

Baseline evaluations (Standard of Care for Bronchoscopy procedures) are to be conducted within 1 week prior to the procedure. Scans and x-rays are usually done ≤ 3 months prior to the start of procedure, this timeframe will be at the discretion of the PI. If the participant's condition is deteriorating, laboratory evaluations should be repeated within 24 hours prior to initiation of the procedure at the discretion of the PI.

Lab tests taken before the procedure are part of the standard of care. Blood collection will not differ from the usual amounts required for conducting the preanesthetic consultation. A negative blood or urine pregnancy test is required prior to performing the procedure as it involves low dose radiation.

Typical follow-up consultations for standard bronchoscopy procedures are done 1 week. If biopsy is benign or non-diagnostic then the patients will be followed at 4 weeks, and 24 weeks after the procedure but may vary depending on the subject's final diagnosis, underline conditions, further treatment, and PI/Investigator preference.

During the follow-up time, subjects will receive phone calls from the study team to check on the subjects well-being and to remind him/her of any future appointments.

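### Day-30 complication contact is scheduled only after a benign or non-diagnostic biopsy, so late complications can be ascertained differently in the two arms

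*Combined protocol and SAP*

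**What the plan says.** Section 3.6 sets the post-discharge contacts. At 30 ± 7 days: "For patients that continue in the study due to a benign or non-diagnostic biopsy, information related to any additional procedural complications" will be collected, with pneumothorax and pneumonia as the examples. The 10 ± 4 day contact has the same condition: it applies to patients who continue "due to a benign or non-diagnostic biopsy. This visit may be completed as a hospital visit, virtual visit or telephone contact". That paragraph adds that, for subjects who have had further interventions or treatment for the nodule, "data regarding their interventions will be collected for the study but information related to complications will not be collected".

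Section 10 agrees with Section 3.6 on the later contact: "If biopsy is benign or non-diagnostic then the patients will be followed at 4 weeks, and 24 weeks after the procedure". It places no such condition on the early one: "Typical follow-up consultations for standard bronchoscopy procedures are done 1 week". It also mentions study-team calls about well-being during follow-up, with no fixed day.

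Section 7 is general: "All device and/or procedure related adverse events will be recorded", from the index procedure "and for a period of 30 days post-procedure". It sets no condition on the biopsy result. On causality, "The PI will assess if there is a relationship of an adverse event to the procedure, as related or not related".

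Three other places bear on the point. Section 1.3 makes the between-group comparison of complications a secondary objective. Section 5.7 does not list a malignant result among the reasons for leaving the study. Section 13.6 says complications will be recorded but gives no time window, denominator or test.

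**The concern.** A patient with a malignant biopsy stays on study, and Section 7 applies to that patient for 30 days, but no section schedules a day-30 contact. The sections can be read together as active contact for some patients and passive recording for the rest. On that reading, how a late event is found still depends on the biopsy result.

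That result arises after randomisation and is what the trial expects CBCT to change. If at least part of the yield gain consists of malignant diagnoses, fewer CBCT patients will be asked about complications at day 30. With all patients as denominator, late events in that arm can be under-counted relative to NB alone, which favours the experimental arm. With only the assessed patients as denominator, the groups compared are selected on a post-randomisation outcome. The trial is nonblinded and the principal investigator judges relatedness, so uneven passive capture is a weak basis for the comparison.

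**Working it through.** **Design figures.** Section 13 gives 67% yield for navigation alone and a 20-point target, hence 67% versus 87%. Section 13.2 gives 68 per arm, 80% power, two-sided 0.05 and an uncorrected chi-squared test. The plan's sample size reproduces on these inputs:

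n = [1.96·√(2·0.77·0.23) + 0.8416·√(0.67·0.33 + 0.87·0.13)]² / 0.20² = 68.3, rounded up to 69 per arm. Power with 68 per arm is 79.8%. So 67% versus 87% is a fair reading of the design alternative. The sample size is not in dispute here.

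**Who loses the contact.** Section 13.1 counts specific benign results as diagnostic, so only malignant diagnoses fall outside the day-30 contact. Let m be the malignant share of diagnostic biopsies, taken as equal in both arms. The documents give no value, so 0.50, 0.75 and 1.0 are shown.

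Expected patients assessed at day 30 = 68 × (1 − m × yield).

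| m | NB alone | CBCT | Ratio CBCT:NB |
|---|---|---|---|
| 0.50 | 68 × 0.665 = 45.2 | 68 × 0.565 = 38.4 | 0.85 |
| 0.75 | 68 × 0.4975 = 33.8 | 68 × 0.3475 = 23.6 | 0.70 |
| 1.0 | 68 × 0.33 = 22.4 | 68 × 0.13 = 8.8 | 0.39 |

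If none of the yield gain is malignant, the numbers assessed are equal and the ratio is 1.0.

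**Effect on the apparent risk ratio.** Assume the true late risk is the same in both arms and does not depend on the biopsy result. Let c be the share of late events in uncontacted patients that is still recorded under Section 7. Then

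observed ratio = [1 − 0.87m(1 − c)] / [1 − 0.67m(1 − c)].

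- c = 0: 0.85, 0.70 and 0.39 for the three shares, as in the table. These are bounds.
- c = 0.5 (assumption): 0.7825/0.8325 = 0.94; 0.67375/0.74875 = 0.90; 0.565/0.665 = 0.85.
- c = 1: 1.0 throughout.

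**Effect in events.** With c = 0, the spurious difference per arm is 68 × r × m × 0.20, where r is the late risk (assumed).

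| r | m = 0.50 | m = 0.75 | m = 1.0 |
|---|---|---|---|
| 1% | 0.07 | 0.10 | 0.14 |
| 5% | 0.34 | 0.51 | 0.68 |

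The 5% is deliberately high. Section 2.1 gives 0.02% to 4.9% for transbronchial pneumothorax over the whole procedure, and no pneumonia rate is given.

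**Patients without a scheduled day-30 contact, both arms together.** 68 × m × (0.67 + 0.87) = 52.4, 78.5 and 104.7 of 136.

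**The case against.** The strongest reply is that a general duty to record plus a visit schedule is not a contradiction. Section 7 covers every patient for 30 days. Section 10's 1-week consultation is not limited by result and falls inside the 10 ± 4 day window. Intra-procedural and pre-discharge events, including those on the chest x-ray, are collected in everyone, and the study team also makes well-being calls. This stands in part: it confines the gap mainly to the period from about week 2 to day 30. It does not close the gap. The calls have no fixed day, do not name complications, and may not reach patients with a malignant biopsy. Section 5.6 otherwise follows only subjects removed for an adverse event that is already known.

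The large ratios are also open to challenge. The 0.39 needs every diagnosis to be malignant and nothing captured outside visits, which is not realistic: benign diagnoses count towards yield, and Section 3.3 admits lesions with a malignancy probability from 0.05. At a malignant share of 0.25 with no other capture, the ratio is already 0.94 (0.7825/0.8325). This is accepted. The 0.39 is a bound, not an estimate.

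Finally, the direction depends on how one sentence in the day-10 paragraph is read. The natural reading excludes complications of a later intervention. A stricter reading excludes all complication information from any subject who had one. As an extreme, suppose m = 0.50 and every non-diagnostic patient has a further intervention before contact. Only benign diagnoses then remain assessed: 68 × 0.67 × 0.50 = 22.8 for NB alone and 68 × 0.87 × 0.50 = 29.6 for CBCT, which reverses the direction. That reading is less natural, and it would add a second result-dependent gap rather than remove the first.

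**Conclusion.** The concern holds. Sections 3.6 and 10 tie active day-30 ascertainment to the biopsy result, Section 7 does not, and ascertainment of late complications can therefore differ by arm. The documents do not fix the size, which depends on the malignant share of the yield gain and on how much is captured without a scheduled contact. With half of the otherwise missed events recorded, the apparent ratio is 0.94 to 0.85 over the shares shown. In events the effect is below one per arm throughout, and Section 13.6 names no test that it could tip. This is a minor to moderate weakness in a secondary comparison. It should be fixed because the fix is cheap and because late events not sought at the time may not be recoverable at analysis.

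**What to change.** Reconcile Sections 3.6, 7 and 10 so that complications of the study procedure are recorded through day 30 in the same way for every patient in both arms, whatever the biopsy result. A telephone contact is enough. Keep the benign or non-diagnostic condition only for the 180-day nodule follow-up.

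State that the existing exclusion of complications from later interventions applies equally to all patients, including those treated after a malignant biopsy. Record the date of any later intervention and use Section 7's related/not-related assessment to separate the two sources.

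In Section 13.6, define the comparison as 30-day complications with all patients in the assigned arm as denominator.

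The cost is protocol wording plus one day-30 call per patient with a malignant biopsy: about 52 to 79 calls at malignant shares of 0.50 to 0.75, and 105 at a share of 1.0. If the day-10 contact is opened to these patients as well, there are at most two calls each: 105 to 157, and 209 at a share of 1.0. Section 3.6 already allows telephone at day 10. No procedure is added and the sample size does not change.
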